6. Meeting criteria for S/SC/F-CDI within 24 hours of planned trial enrollment, which we define as any one of the following: (1) leukocytosis with peripheral WBC $\geq 15,000$ cells/mL; (2) hypotension with systolic blood pressure sustained < 90 mmHg for three or more hours or requiring pressors; (3) provider documentation of ileus or radiologic evidence of bowel dilation or megacolon; (4) acute kidney injury with increase in baseline serum creatinine level by $\geq 50\%$ or new dialysis initiation; (5) serum lactate > 2.2 mmol/L; or (6) ≥ 3 systemic inflammatory response syndrome (SIRS) criteria (which include heart rate > 90 beats per minute, respiratory rate > 20 breaths per minute or $\text{PaCO}_2 < 32$ mmHg, temperature $> 38^\circ\text{C}$ or $< 36^\circ\text{C}$, WBC $> 12,000$ cells/uL, $< 4,000$ cells/uL, or $> 10\%$ immature (band) forms).
7. Receipt of FMT or enrollment in a clinical trial for FMT within the last 3 months.

Investigational Product	
1. Penn Microbiome Therapy – 001 (PMT-001): no more than 152 mL suspension for rectal enema from 40g human stool, comprising a total of 1×10^8 – 1×10^{12} anaerobic bacterial CFUs/dose.2. Penn Microbiome Therapy – 002 (PMT-002): no more than 152 mL suspension for intragastric, intraduodenal, or intrajejunal administration from 40g human stool, comprising 1×10^8 – 1×10^{12} anaerobic bacterial CFUs/dose.3. Penn Microbiome Therapy – 003 (PMT-003): no more than 32 capsules for oral administration from 40g donated stool, comprising 1×10^8 – 1×10^{12} anaerobic bacterial CFUs/dose.
	PMT-001, PMT-002, PMT-003, are packaged for single-dose administration.
Duration of administration	10 – 90 minutes (target 30 minutes)
Reference therapy	Single dose of Penn Microbiome Therapy product.
Statistical Methodology	Primary outcome will be resolution of diarrhea without recurrence assessed at 8 weeks (56 days) after intervention. Logistic regression analysis will be used to assess if repeat dosing is superior to single dose.
Safety Evaluations	We will monitor safety of administration as well as safety of the investigational products, in terms of adverse events as listed in Section 9 .
Data and Safety Monitoring Plan	See Section 10 .

Background and Study Rationale

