8.3. Sample Size and Power Determination

The primary analysis will be stratified based on the most recent positive CDI test (NAAT versus EIA) prior to enrollment. Given the anticipated enrollment of 300 subjects (150 per intervention group), a conservative estimate that 10% of subjects will be lost to follow-up (i.e., minimum subject number 90% of total), and the expectation that the ratio of EIA-positive/NAAT-positive subjects will be 1:2, the expected sample size will be 90 for EIA and 180 for NAAT ($150*0.9=135$ per arm, with a 45:90 ratio for EIA/NAAT). The low-dose cure rate is anticipated to be about 50% in the NAAT group and 70% in the EIA group. Based on these assumptions, the detectable difference between the cure rates for the low and high dose groups for 80% power and varying type I error rates, based on a Chi-square test (two-sided), are provided below.

Stratified Population	Number of subjects (subjects per arm)	Type 1 Error	Power	Detectable difference in proportions compared to 50%
EIA	90 (45)	0.05	0.8	0.7725
EIA	90 (45)	0.1	0.8	0.7458
EIA	90 (45)	0.2	0.8	0.7133
NAAT	180 (90)	0.05	0.8	0.7003
NAAT	180 (90)	0.1	0.8	0.6793
NAAT	180 (90)	0.2	0.8	0.6543

For phase II studies it is typical to accept a type 1 error of greater than 0.05 (Schoenfeld 1980; Khan 2012). For this phase II study, we will accept a difference between intervention groups that meets a type I error threshold of 0.2. Therefore, we will have 80% power to detect a difference of 0.2133 (50% to 71.33%) in the EIA group, and a difference of 15.43% (50% to 65.43%) in the NAAT group. The power calculations were performed using PASS 16 (Power Analysis and Sample Size Software (2018). NCSS, LLC. Kaysville, Utah, USA, ncss.com/software/pass/).

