8.4.2. Efficacy Analysis

An intention to treat analysis will be performed for the primary outcome of clinical resolution of diarrhea without recurrence in subjects with R-CDI at 8 weeks following FMT. A logistic regression model will be used to compare the two study groups (single-dose versus double-dose) to detect superiority of a dose. A p-value (one-sided) of <0.2 will be considered significant. As above, the primary analysis will be stratified based on the most recent positive CDI test (NAAT versus EIA) prior to enrollment. Per protocol analysis will also be performed, based on received (rather than randomized) treatment.

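### Power in Section 8.3 is calculated for a two-sided test at 0.2, but Section 8.4.2 declares success at one-sided p<0.2, so the stated power belongs to a different decision rule

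*Combined protocol and SAP*

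**What the plan says.** Section 8.3 introduces its table of detectable cure rates as "based on a Chi-square test (two-sided"), at 80% power and type I error rates of 0.05, 0.1 and 0.2. It then adopts the last of these: "we will accept a difference between intervention groups that meets a type I error threshold of 0.2". From that it concludes 80% power for 50% against 71.33% in the EIA group (45 per arm) and for "a difference of 15.43% (50% to 65.43%) in the NAAT group" (90 per arm).

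Section 8.4.2 specifies a logistic regression comparing the arms "to detect superiority of a dose" and gives the only p-value rule in the document: "A p-value (one-sided) of <0.2 will be considered significant".

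The Study Summary (Statistical Methodology) gives a direction but no alpha or sidedness: "Logistic regression analysis will be used to assess if repeat dosing is superior to single dose".

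On base rates, Section 8.3 says: "The low-dose cure rate is anticipated to be about 50% in the NAAT group and 70% in the EIA group". Its table nevertheless heads the result column for both groups "Detectable difference in proportions compared to 50"%.

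**The concern.** A two-sided test at 0.2 puts 0.10 in each tail. A one-sided test at 0.2 puts all 0.20 in the favourable tail. These are different cut-offs, and nothing in the document says that Section 8.3 was meant as a deliberately conservative calculation for the looser rule.

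The threshold decides whether the primary result counts as positive. Section 8.3 words its 0.2 as an acceptance criterion, directly after a two-sided table. Section 8.4.2 words its 0.2 as a one-sided significance rule. In an open-label trial, a result falling between the two cut-offs could be called positive or negative with support from the protocol either way. Readers would also take the 80% power and the 0.2 error rate as properties of the test to be run.

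**Working it through.** **Inputs.** From Section 8.3: 90 per arm (NAAT) and 45 per arm (EIA) after 10% loss; table reference rate 50%; anticipated single-dose rates 50% (NAAT) and 70% (EIA); type I error 0.2; two-sided chi-square test. From Section 8.4.2: one-sided p<0.2. From Section 3.1.5: 1:1 allocation.

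**Formula.** Normal approximation with unpooled variance:

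power = Φ(Δ/SE − z), where SE = √{[p₁(1−p₁) + p₂(1−p₂)]/n}.

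Critical values: two-sided 0.2, z = 1.2816; one-sided 0.2, z = 0.8416.

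**Step 1: reproduce the table.** The NAAT row at 0.2 gives SE = √[(0.25 + 0.6543×0.3457)/90] = 0.07274 and Δ/SE = 0.1543/0.07274 = 2.121. Two-sided power is Φ(2.121 − 1.282) = 0.80. All rows:

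| Row | Rate | Power, two-sided | Power, one-sided at same alpha |
|---|---|---|---|
| EIA 0.05 | 0.7725 | 0.800 | 0.876 |
| EIA 0.1 | 0.7458 | 0.800 | 0.886 |
| EIA 0.2 | 0.7133 | 0.800 | 0.900 |
| NAAT 0.05 | 0.7003 | 0.800 | 0.876 |
| NAAT 0.1 | 0.6793 | 0.800 | 0.886 |
| NAAT 0.2 | 0.6543 | 0.799 | 0.900 |

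The two-sided label is therefore not a slip; the table was computed that way. Pooled variance gives slightly lower two-sided figures for the two 0.2 rows (0.791 EIA, 0.795 NAAT) and leads to the same conclusion.

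**Step 2: apply the Section 8.4.2 rule to NAAT.** At 65.43%, power is Φ(2.121 − 0.842) = 0.900 (pooled 0.898; exact binomial enumeration 0.900). The rate detectable with 80% power is 62.35% unpooled or 62.40% pooled, against 65.43% in the plan.

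**Step 3: EIA.** On the table's 50% reference, the 80%-power rate moves from 71.33% to about 67.2% through sidedness alone. From the anticipated 70%, it is 87.8% under two-sided 0.2 (pooled 88.0%) and 84.6% under one-sided 0.2 (pooled 84.7%). Exact power at those unpooled rates is about 0.80 in both cases.

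**Step 4: false-positive rate in favour of double dose, per stratum test.**

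| | One-sided 0.2 | Two-sided 0.2 |
|---|---|---|
| Nominal | 0.20 | 0.10 |
| Exact, NAAT at 50% | 0.206 | 0.102 |
| Exact, EIA at 70% | 0.210 | 0.104 |

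If the planned stratification means two separate tests, the nominal chance of at least one false positive for double dose is 1 − 0.8² = 0.36 against 1 − 0.9² = 0.19.

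**Step 5: results on which the thresholds disagree** (pooled chi-square).

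| Single dose | Double dose | One-sided p | Two-sided p |
|---|---|---|---|
| NAAT 45/90 | 51/90 | 0.185 | 0.370 |
| NAAT 45/90 | 52/90 | 0.148 | 0.295 |
| NAAT 45/90 | 53/90 | 0.116 | 0.231 |
| EIA 32/45 | 36/45 | 0.163 | 0.327 |
| EIA 32/45 | 37/45 | 0.106 | 0.213 |

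Each is positive under Section 8.4.2 and not significant at the level powered in Section 8.3. Logistic regression Wald p-values agree closely (two-sided 0.370, 0.296 and 0.232 for NAAT; 0.329 and 0.216 for EIA).

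**The case against.** The best defence has four parts.

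- **Total alpha is unchanged.** In the Study Summary's direction, one-sided p<0.2 has a total type I error of 0.2, the number Section 8.3 accepts. Section 8.3 nowhere states 10% for double dose. This is correct, and the doubling claimed here concerns only the double-dose direction. That is still the direction in which the trial would claim success. The defence also depends on fixing the direction, because Section 8.4.2 does not say which dose is to be superior. If the one-sided rule were applied whichever way the data pointed, the total would be 0.4.
- **The error is conservative for power, and Section 8.4.2 holds the only p-value rule.** Both are true, and the trial loses no power. But the acceptance sentence in Section 8.3 also reads as a decision criterion, so the rule is not settled beyond argument.
- **Phase II trials tolerate a high alpha.** Section 8.3 makes that argument for 0.2 beside a two-sided table. It does not extend it to the equivalent of two-sided 0.4.
- **The EIA base rate and multiplicity are separate issues.** In origin they are. The EIA rows come in because the same table has to be restated. The 36% and 19% figures are conditional on two separate tests, and the conclusion does not depend on them.

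**Conclusion.** The concern holds, and the plan must be corrected before analysis. The 80% power in Section 8.3 is correct for a two-sided test at 0.2 against 50%, but the plan declares success by a different test. Under the declared rule, NAAT power at 65.43% is about 90%, the 80%-power rate is about 62.4%, and the nominal false-positive rate for double dose is 20% per test instead of 10%. With 45/90 single-dose cures, three possible double-dose counts (51 to 53) change verdict; with 32/45 in EIA, two do (36 and 37).

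These figures assume the Section 8.3 sample sizes and base rates, a comparison within each stratum, and the Study Summary's direction. The document does not say whether stratification means two tests or one adjusted model. The sidedness conflict exists under either reading.

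**What to change.** Use one sidedness and one alpha in Sections 8.3 and 8.4.2, and state in Section 8.4.2 that the hypothesis is superiority of repeat dosing over single dose, as in the Study Summary. There are two ways to do it.

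- **(a)** Change Section 8.4.2 to two-sided p<0.20, equivalent to one-sided p<0.10 for double dose. The NAAT figure of 65.43% then stands. The price is a stricter success threshold.
- **(b)** Keep one-sided p<0.20 and restate Section 8.3 for it: NAAT about 62.4% at 80% power, or about 90% power at 65.43%. The price is openly accepting a 20% nominal false-positive rate per test in favour of double dose.

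Under either option, recompute the EIA rows from the anticipated 70%. At the 0.2 level the detectable rate is about 87.8% under (a) or 84.6% under (b), that is, differences of about 18 or 15 points. The 71.33% figure should not be carried forward: it is calculated against 50% and lies only 1.33 points above the anticipated single-dose rate. Losing it follows from the base rate, not from the choice of sidedness.

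Both options are text changes. Neither alters the target of 300 subjects.

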3.1.5. Allocation to Interventional Group

Stratified randomization will be performed in a 1:1 fashion (one to single-dose and one to double-dose). The stratification will be by route of delivery, which will be decided on following enrollment but prior to randomization. The route of administration (i.e., PMT-001 versus PMT-002 versus PMT-003) will be determined by counsel from the subject's referring health care provider and the subject's own preference. The randomization strata will include: upper delivery (PMT-002 or PMT-003) or lower delivery (PMT-001). Stratified randomization by route will be performed in order to ensure balance in route of delivery between the two groups. The randomization schedule will be prepared using a random-size block strategy to ensure balance throughout the trial. Prior to enrollment of the first subject, a randomization table will be produced for each category using Stata statistical software and the "Ralloc" package. There is no randomization to a no-FMT control because FMT is already guideline-recommended for the treatment of R-CDI (McDonald 2018).

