8.1. Primary Endpoint

The primary endpoint will be proportion of subjects with clinical resolution of diarrhea without recurrence in subjects with R-CDI at 8 weeks (56 days) following FMT. To address the potential for misclassification of subjects who are only NAAT-positive for *C. difficile* (McDonald 2018), the primary analysis will be stratified based on the most recent positive CDI test (NAAT versus EIA) prior to enrollment.

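### Section 8.4.2 sets one dose comparison at one-sided 0.2, but Section 8.3 powers two separate two-sided stratum tests, and no rule says how the two strata would answer the one question

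*Combined protocol and SAP*

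**What the plan says.** - **The question.** Section 2.1 and the synopsis ask one thing: whether two doses do better than one. Section 8.4.2 matches this: "A logistic regression model will be used to compare the two study groups (single-dose versus double-dose) to detect superiority of a dose". It gives one threshold: "A p-value (one-sided) of <0.2 will be considered significant".
- **The stratification.** Section 8.4.2 continues that "the primary analysis will be stratified based on the most recent positive CDI test (NAAT versus EIA) prior to enrollment". Sections 8.1 and 8.3 say the same. Section 8.1 gives the reason: "To address the potential for misclassification of subjects who are only NAAT-positive". No section says whether test type is a covariate in one model or the basis for two tests.
- **The power.** Section 8.3 states "we will accept a difference between intervention groups that meets a type I error threshold of 0.2" and uses a two-sided chi-square test. Its table treats EIA (45 per arm) and NAAT (90 per arm) as separate populations and concludes: "Therefore, we will have 80% power to detect a difference of 0.2133 (50% to 71.33%) in the EIA group, and a difference of 15.43" percent in the NAAT group. It gives no figure for all 270 evaluable subjects.
- **The control rates.** The same section says "The low-dose cure rate is anticipated to be about 50% in the NAAT group and 70% in the EIA group", yet every table row is compared with 50%.
- **The randomization.** Section 3.1.5: "The randomization strata will include: upper delivery (PMT-002 or PMT-003) or lower delivery (PMT-001"). EIA/NAAT is not a randomization stratum, and 8.4.2 does not mention route.

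**The concern.** The analysis section and the power section describe different tests. They differ in number (one or two), in sidedness, and for EIA in the control rate.

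If 8.4.2 governs, the sponsor has not stated what its primary test can detect. If the layout of 8.3 governs, the plan has two results and one question, with no rule for the case where one stratum meets the threshold and the other does not. The same data could then be reported as positive or negative, depending on a choice that is not yet written down.

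**Working it through.** **Inputs.** From 8.3: 45 EIA and 90 NAAT subjects per arm after 10% loss; single-dose cure 70% (EIA) and 50% (NAAT); 80% power. Alpha is one-sided 0.2 (8.4.2) or two-sided 0.2 (8.3). Two-sided 0.2 allows 0.1 in the direction of double dose. Critical values: z = 0.8416 for one-sided 0.2, 1.2816 for two-sided 0.2, and 0.8416 for 80% power. The 12/12 and 15/0 effects (EIA/NAAT, in points) are illustrations, not figures from the plan.

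**1. Reproduce 8.3.** Power = Φ(d/SE − z), with SE² = [p1(1−p1) + p2(1−p2)]/n.
- EIA, 0.50 to 0.7133, n = 45: SE = √[(0.2500 + 0.2045)/45] = 0.1005; 0.2133/0.1005 − 1.2816 = 0.84, so power is 80%.
- NAAT, 0.50 to 0.6543, n = 90: SE = √[(0.2500 + 0.2262)/90] = 0.0727; 0.1543/0.0727 − 1.2816 = 0.84, so power is 80%.

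All six table rows reproduce to within 0.0001 as two-sided tests within one stratum. At one-sided 0.2 the detectable rates would be 0.672 and 0.624, so the table is not on the basis of 8.4.2.

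**2. EIA from the plan's own 70%.** The same formula at two-sided 0.2 (one-sided 0.1) gives 17.8 points (70% to 87.8%), against the stated 21.3.

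**3. One adjusted test on all 270.** Weights are 90/270 = 1/3 (EIA) and 180/270 = 2/3 (NAAT); SE² = (1/9)SE²(EIA) + (4/9)SE²(NAAT).
- One-sided 0.2: SE = 0.0578; d = (0.8416 + 0.8416) × 0.0578 = 9.7 points.
- Two-sided 0.2: SE = 0.0572; d = (1.2816 + 0.8416) × 0.0572 = 12.2 points (0.1215; 0.1221 with pooled null variance).

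Those assume a common risk difference. A logistic dose term assumes a common odds ratio. Setting ln(OR) × √I equal to the same sums of z, where I adds the information from the two strata:
- One-sided 0.2: OR about 1.54, which is 8.2 points in EIA and 10.6 in NAAT.
- Two-sided 0.2: OR about 1.73, which is 10.2 and 13.4 points.

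**4. Two tests: false claim for double dose when there is no effect.**

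| Basis | One test | Either stratum counts | Both required |
|---|---|---|---|
| One-sided 0.2 (8.4.2) | 20% | 1 − 0.8² = 36% | 0.2² = 4% |
| Two-sided 0.2 (8.3) | 10% | 1 − 0.9² = 19% | 0.1² = 1% |

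**5. Two tests: how often the strata split, with 12 points in both.**
- One-sided 0.2: stratum power 0.693 (EIA) and 0.786 (NAAT). Either 0.934, both 0.545, split 0.934 − 0.545 = 39%.
- Two-sided 0.2: stratum power 0.526 and 0.638. Either 0.828, both 0.335, split 49%.
- No effect, one-sided 0.2: 0.36 − 0.04 = 32%.

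**6. Power of one test (one-sided 0.2) against one-sided 0.1 in each stratum, either counting.**
- 12/12 points: 90% against 83%.
- 15/0 points: the average effect is 15/3 = 5 points and SE = 0.0575, so power is Φ(0.870 − 0.842) = 51%. The split gives 1 − (1 − 0.674)(1 − 0.1) = 71%.

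**The case against.** The best defence is that a stratified analysis conventionally means one stratum-adjusted test. Section 8.4.2 names one model, one threshold and the stratifying variable. On that reading the split results and the 36% disappear. This is a fair reading and may be what was intended. It still leaves 8.3 powering a different test at a different sidedness. The separate populations in 8.3, and the reason given in 8.1, also keep the two-test reading open: a test-type covariate adjusts baseline risk but does not undo dilution of the dose effect in misclassified NAAT subjects.

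A reader might infer three stronger things that the documents do not support.
- **That the plan carries a 36% error rate.** This needs an either-stratum rule that the plan does not state, plus the layout of 8.3 at the alpha of 8.4.2. Nor should 36% be set against the two-sided 0.2 of 8.3. Like with like is 36% against 20%, or 19% against 10%.
- **That the trial is undersized, or that one test always does better.** One adjusted test detects a smaller difference than either stratum test when the effects are similar. At 15/0 points it has less power than the split.
- **That the choice will be made by someone who has seen the data.** Section 5.6 says only that subjects and investigators are unblinded, and 8.4.3 plans no interim analysis. The documents do not say when the analyst sees data by arm.

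Omitting route does not cause the ambiguity. It is a gap to close in the same edit.

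**Conclusion.** The point holds as a mismatch between 8.3 and 8.4.2 and a missing decision rule. On the conventional reading, the stated 21.3 and 15.4 points do not belong to the primary test, which detects about 9.7 points (one-sided 0.2) or 12.2 (two-sided 0.2) as a common difference. On the two-test reading, a split result is common and has no stated meaning.

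These sizes rest on the plan's stratum sizes, 10% loss, cure rates of 70% and 50%, similar effects in both strata where a common effect is quoted, and normal approximations. Route is not in the figures because the documents give no cure rates by route. The plan should be corrected before analysis; nothing here calls for a change in size or conduct.

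**What to change.** Before any data by arm are seen, state in 8.1 and 8.4.2 that the primary test is the dose term of one logistic model adjusted for CDI test type (EIA/NAAT) and randomized route stratum (upper/lower), judged once. Make the EIA and NAAT estimates with confidence intervals, and the dose-by-test-type interaction, secondary.

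Use the same alpha and sidedness in 8.3 and restate its power for that test, labelled as 270 evaluable subjects with bases of 70% and 50%:
- one-sided 0.2: odds ratio about 1.54 (about 8 points in EIA and 11 in NAAT);
- two-sided 0.2: odds ratio about 1.73 (about 10 and 13 points).

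If the sponsor intends stratum-specific claims instead, which is its decision, state an alpha and success rule for each stratum so that the total matches the overall one-sided error it adopts. One-sided 0.1 each gives about 19% (0.20 in simulation, because counts are discrete), acceptable only if the overall standard is one-sided 0.2. The NAAT figure of 15.4 points then stands, and the EIA figure must be recomputed from 70% (about 17.8 points).

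**Cost.** Wording in 8.1, 8.3 and 8.4.2. With one test, stratum results lose primary status, and power falls if the effect is diluted in NAAT subjects. With two tests, power is lower when the strata respond alike, and the detectable differences are larger.

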8.4.3. Interim Analysis

No interim analysis is planned.

8.4.4. Safety Analysis

All subjects entered into the study and randomized will have detailed information collected on adverse events starting at enrollment and for the duration of follow-up, as described elsewhere. The primary safety endpoints of frequency of AEs, SAEs, and AESIs will be described.

- sepsis or shock (temperature, heart rate, or blood pressure change as already described) – PMT-001, 002, and 003
- bowel injury (abdominal pain change as already described) – PMT-001, 002, and 003

- aspiration (respiratory rate or oxygen saturation change as already described) – PMT-002 and 003 only

In the subsequent, 7-day monitoring period following administration of investigational product, subjects will be monitored with close attention to the following:

- donor-derived infection (temperature or abdominal pain change as already described) – PMT-001, 002, and 003
- worsening CDI (temperature, change in stool frequency/quantity or abdominal pain, or emesis as already described) – PMT-001, 002, and 003

In the subsequent, 30-, 56-, 90-, and 180-day monitoring periods, subjects will be monitored with close attention to the following:

- transmitted infection (temperature or abdominal pain change as already described) – PMT-001, 002, and 003
- recurrent CDI (temperature, change in stool frequency/quantity or abdominal pain, or emesis as already described) – PMT-001, 002, and 003
- metabolic changes (polydipsia, polyuria, weight gain or weight loss) – PMT-001, 002, and 003

